13.4 CONFIDENTIALITY AND PRIVACY

Participant confidentiality and privacy is strictly held in trust by the participating investigators, their staff, and the sponsor(s). This confidentiality is extended to cover testing of biological samples and genetic tests in addition to the clinical information relating to participants.

Therefore, the study protocol, documentation, data, and all other information generated will be held in strict confidence. No information concerning the study or the data will be released to any unauthorized third party without prior written approval of the sponsor.

All research activities will be conducted in as private a setting as possible.

The study monitor, other authorized representatives of the sponsor, representatives of the Institutional Review Board (IRB), and/or regulatory agencies may inspect all documents and records required to be maintained by the investigator, including but not limited to, medical records (office, clinic, or hospital) and pharmacy records for the participants in this study. The clinical study site will permit access to such records.

The study participant's contact information will be securely stored at the/each clinical site for internal use during the study. At the end of the study, all records will continue to be kept in a secure location for as long a period as dictated by the reviewing IRB, Institutional policies, or sponsor requirements.

Study participant research data, which is for purposes of statistical analysis and scientific reporting, will be transmitted to and stored at the NCI CCR. This will not include the participant's contact or identifying information. Rather, individual participants and their research data will be identified by a unique study identification number. The study data entry and study management systems used by the clinical site(s) and by NCI CCR research staff will be secured and password protected. At the end of the study, all study databases will be archived at the NCI CCR.

To further protect the privacy of study participants, a Certificate of Confidentiality has been issued by the National Institutes of Health (NIH). This certificate protects identifiable research information from forced disclosure. It allows the investigator and others who have access to research records to refuse to disclose identifying information on research participation in any civil, criminal, administrative, legislative, or other proceeding, whether at the federal, state, or local level. By protecting researchers and institutions from being compelled to disclose information that would identify research participants, Certificates of Confidentiality help achieve the research objectives and promote participation in studies by helping assure confidentiality and privacy to participants.

14 PHARMACEUTICAL AND INVESTIGATIONAL DEVICE INFORMATION

14.1 IBRUTINIB (IND # 146697)

14.1.1 Description

Ibrutinib is a small-molecule tyrosine kinase inhibitor with a molecular weight of 440.50 g/mole (anhydrous basis). The CAS name for ibrutinib is 1-[(3R)-3-[4-amino-3-(4-phenoxyphenyl) -Hpyrazolo[3,4-d]pyrimidin-1-yl]piperidin-1-yl]prop-2-en-1-one. The molecular formula of ibrutinib is C₂₅H₂₄N₆O₂

Chemical Structure of Ibrutinib:

Ibrutinib is a white to off-white solid. Ibrutinib has a single chiral center and the absolute configuration at the stereocenter is (R).

14.1.2 Source

Pharmacyclics will supply investigational ibrutinib 140 mg capsules. Ibrutinib comes packaged as 92-count and 120-count bottle sizes of 140 mg ibrutinib capsules. All unused capsules at the end of the month will be brought back and disposed.

Pharmacyclics will supply drug free of charge. The initial drug shipment will be sent by Pharmacyclics to the NIH and any participating sites. Each pharmacy will be responsible for all subsequent drug orders.

14.1.3 Formulation and Preparation

Ibrutinib capsules are provided as a hard gelatin capsule containing 140 mg of ibrutinib. All study drug will be dispensed in child-resistant packaging.

14.1.4 Stability and Storage

The PI or their designee is responsible for taking an inventory of each shipment of study drug received and comparing it with the accompanying study drug accountability form. The PI or their designee will verify the accuracy of the information on the form, sign and date it, retain a copy in the study file, and return a copy to Pharmacyclics.

At the study site, all investigational study drugs will be stored in a locked, safe area to prevent unauthorized access. The study drug should be stored at room temperature away from direct sunlight and protected from excessive heat and cold.

14.1.5 Administration procedures

See Section [3.2](#).

14.1.6 Expected Toxicities

See Section [1.2.2.4](#) and [Appendix L](#).

14.1.7 Incompatibilities

The use of strong CYP3A inhibitors/inducers, and grapefruit and Seville oranges should be avoided for the duration of the study. Please see table in section [Error! Reference source not found.](#) for further details on dosing with CYP3A inhibitors.

When anti-fungal agents, that have CYP3A properties are discontinued, the ibrutinib dose should be increased to 420 mg.

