3.2.1 Dose Adjustments for participants on CYP3A4 inhibitors

Participants who are treated with certain medications that are mild and moderate CYP3A4 inhibitors will start ibrutinib at a lower dose.

A list of common CYP3A inhibitors and inducers is provided in [Appendix C](#). For further information, please refer to the current version of the ibrutinib IB and examples of inhibitors, inducers, and substrates can be found at <http://medicine.iupui.edu/clinpharm/ddis/main-table/>.

Drug	Ibrutinib dose modification
• Mild CYP3A inhibitors	420 mg once daily. No dose adjustment required
• Moderate CYP3A inhibitors	420 mg once daily. No dose adjustment required
• Voriconazole at any dose or • Posaconazole at doses less than or equal to suspension 200 mg BID	280 mg once daily
• Posaconazole suspension 200 mg TID or 400 mg BID • Posaconazole IV injection 300 mg once daily • Posaconazole delayed-release capsules 300 mg once daily	140 mg once daily
• Other strong CYP3A inhibitors	Avoid concomitant use. If these inhibitors will be used short-term (such as anti-infectives for seven days or less), interrupt IMBRUVICA

If these medications are later discontinued, ibrutinib dose may be increased to 420 mg.

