3.3.2 Dose Modification for Adverse Reaction

Dose reductions will be required for any of the following toxicities:

- Grade 3 ANC (< 1,000/ μ L) with an associated temperature $\geq 38.5^{\circ}\text{C}$
- Grade 4 ANC (< 500/ μ L) for more than 7 days
- Grade 3 thrombocytopenia (< 50,000/ μ L) in the presence of clinically significant bleeding events
- Grade 4 thrombocytopenia (< 25,000/ μ L)
- Grade 3 or 4 nausea, vomiting, or diarrhea despite optimal anti-emetic and/or anti-diarrheal therapy

- Any other Grade 4 or unmanageable Grade 3 toxicity attributed to ibrutinib
- Optional dose reduction can be done also at investigator discretion for any bothersome toxicity

Recommended Dosage Modifications for Adverse Reactions		
Adverse Reaction	Occurrence	Dose Modification after Recovery
Grade 2 cardiac failure	First	Restart at 280 mg daily ^a
	Second	Restart at 140 mg daily ^a
	Third	Discontinue Ibrutinib
Grade 3 cardiac arrhythmias	First	Restart at 280 mg daily ^a
	Second	Discontinue Ibrutinib
Grade 3 or 4 cardiac failure	First	Discontinue Ibrutinib
Grade 4 cardiac arrhythmias		
Other Grade 3 or 4 non-hematological toxicities ^b Grade 3 or 4 neutropenia with infection or fever Grade 4 hematological toxicities	First	Restart at 280 mg daily
	Second	Restart at 140 mg daily
	Third	Discontinue Ibrutinib

^a Evaluate the benefit-risk before resuming treatment

^b For Grade 4 non-hematologic toxicities, evaluate the benefit-risk before resuming treatment

If the dose of ibrutinib is reduced, at the investigator's discretion, the dose of ibrutinib may be re-escalated after 4 weeks of a dose reduction in the absence of a recurrence of the toxicity that led to the reduction.

3.3.2.1 Ibrutinib Dose Modifications – General:

Occurrence	Action to be taken
Hematologic Adverse Events	
First	Withhold ibrutinib until recovery to Grade ≤ 1 or baseline; may restart at the original dose level
Second	Withhold ibrutinib until recovery to Grade ≤ 1 or baseline; may restart at 1 dose level below that for which the toxicity occurs (i.e., 280 mg/day for 420 mg/day dose)

Occurrence	Action to be taken
Third	Withhold ibrutinib until recovery to Grade ≤ 1 or baseline; may restart at 1 dose level below that for which the toxicity occurs (i.e., 140 mg/day for 280 mg/day dose)
Fourth	Discontinue ibrutinib
Non-Hematological Adverse Events	
First	Withhold ibrutinib until recovery to Grade ≤ 1 or baseline; may restart at original dose level

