Second	Withhold ibrutinib until recovery to Grade ≤ 1 or baseline; may restart at 1 dose level below that for which the toxicity occurs
Third	Withhold ibrutinib until recovery to Grade ≤ 1 or baseline; may restart at 1 dose level below that for which the toxicity occurs
Fourth	Discontinue ibrutinib

3.3.2.2 Dose modification for atrial fibrillation:

For Grade 3 or 4 atrial fibrillation or persistent atrial fibrillation of any grade, consider the risks and benefits of ibrutinib treatment. If clinically indicated, the use of anticoagulants or antiplatelet agents may be considered for the thromboprophylaxis of atrial fibrillation.

3.3.2.3 Dose modifications for hepatic impaired subjects:

- Ibrutinib is metabolized in the liver and therefore subjects with clinically significant chronic hepatic impairment at the time of Screening (Child- Pugh class C) are excluded from study participation. Refer to [Appendix J](#) for Child-Pugh classification. For subjects with a direct bilirubin $> 3 \times$ ULN (Grade 3 CTCAE), ibrutinib will be held until the bilirubin returns to $\leq 1.5 \times$ ULN (Grade 1 CTCAE) or baseline. Upon reduction to $\leq 1.5 \times$ ULN ibrutinib will be re-started at one dose level below that for which the toxicity occurs (see [Table 1](#) for dose modification schedule).
- For subjects whose baseline AST/ALT is $\leq 3 \times$ ULN, if ALT or AST increases to $> 5 \times$ ULN (Grade 3 CTCAE) ibrutinib will be held until the ALT/AST value returns to $\leq 3 \times$ ULN (Grade 1 CTCAE) or baseline. Ibrutinib will be re-started at one dose level below that for which the toxicity occurs.
- For subjects whose baseline AST/ALT is between 3 to 5 \times ULN (because of chronic GvHD), if ALT/AST increases to 1.5 \times baseline level then ibrutinib will be held until the ALT/AST value returns to $\leq 3 \times$ ULN or baseline. Ibrutinib will be re-started at one dose level below that for which the toxicity occurs.

Table 1: Ibrutinib Dose Modifications for Hepatic Impairment

Occurrence	Action to be Taken
------------	--------------------

First	Withhold study drug until recovery to Grade ≤ 1 CTCAE or baseline; restart at 1 dose level below that for which the toxicity occurs (280 mg/day for 420 mg/day dose)
Second	Withhold study drug until recovery to Grade ≤ 1 CTCAE or baseline; restart at 1 dose level below that for which the toxicity occurs 140 mg/day for 280 mg/day dose)
Third	Discontinue study drug

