4.4 MEDICATION TO BE USED WITH CAUTION

4.4.1 CYP3A Enzyme Inhibitors/Inducers

Ibrutinib is metabolized primarily by CYP3A4.

A list of common CYP3A inhibitors and inducers is provided in [Appendix C](#). For further information, please refer to the current version of the ibrutinib IB and examples of inhibitors, inducers, and substrates can be found at <http://medicine.iupui.edu/clinpharm/ddis/main-table/>. This website is continually revised and should be checked frequently for updates. Avoid concomitant use of strong CYP3A inducers ([Appendix C](#)). Consider alternative agents with less CYP3A induction and transition to a new agent within 4 weeks of study treatment initiation. Dose modifications for participants on CYP3A4 inhibitors are listed in Section [3.2.1](#).

Avoid grapefruit and Seville oranges during ibrutinib treatment, as these contain moderate inhibitors of CYP3A.

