16.3 APPENDIX C: INHIBITORS AND INDUCERS OF CYP3A

Inhibitors of CYP3A are defined as follows. A comprehensive list of inhibitors can be found at the following website: <http://medicine.iupui.edu/clinpharm/ddis/table.aspx>. The general categorization into strong, moderate, and weak inhibitors according to the website is displayed below. Refer to Section 4.4.1 and 14.1.7 on instructions for concomitant use of CYP3A inhibitors and inducers with study medications.

Inhibitors of CYP3A	Inducers of CYP3A

Strong inhibitors:
 
INDINAVIR NELFINAVIR RITONAVIR CLARITHROMYCIN ITRACONAZOLE KETOCONAZOLE NEFAZODONE SAQUINAVIR TELITHROMYCIN
 
Moderate inhibitors:
 
aprepitant erythromycin diltiazem flucanazole grapefruit juice Seville orange juice verapamil
	
Weak inhibitors:
 
cimetidine
 
All other inhibitors:
 
amiodarone NOT azithromycin chloramphenicol boceprevir ciprofloxacin delavirdine diethyl-dithiocarbamate fluvoxamine gestodene imatinib mibepradil mifepristone norfloxacin norfluoxetine star fruit telaprevir troleandomycin voriconazole
 
Carbamazepine Efavirenz Nevirapine Barbiturates Glucocorticoids Modafinil Oxcarbazepine Phenobarbital Phenytoin Pioglitazone Rifabutin Rifampin St. John's Wort Troglitazone

Source: <http://medicine.iupui.edu/clinpharm/ddis/table.aspx>

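### Section 14.1.7 returns ibrutinib to 420 mg when a CYP3A antifungal stops, with no exception for a dose that was also reduced for toxicity

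*Combined protocol and SAP*

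**What the plan says.** Three parts of the protocol govern the dose of a participant who has been below 420 mg.

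- **Section 14.1.7 (Incompatibilities)**, on stopping an antifungal: "When anti-fungal agents, that have CYP3A properties are discontinued, the ibrutinib dose should be increased to 420 mg".
- **Section 3.2.1**, after its table of ibrutinib doses by CYP3A inhibitor: "If these medications are later discontinued, ibrutinib dose may be increased to 420 mg".
- **Section 3.3.2**, on a dose lowered for an adverse reaction. At the investigator's discretion, the dose "may be re-escalated after 4 weeks of a dose reduction in the absence of a recurrence of the toxicity that led to the reduction".

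Two cross-references bear on which text a site will read. Appendix C directs: "Refer to Section 4.4.1 and 14.1.7 on instructions for concomitant use of CYP3A inhibitors and inducers with study medications". Section 4.4.1 in turn points back to 3.2.1: "Dose modifications for participants on CYP3A4 inhibitors are listed in Section" 3.2.1. Neither adds anything about a dose also reduced for toxicity.

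**The concern.** The two sentences on stopping an inhibitor use different verbs: *should* in 14.1.7 and *may* in 3.2.1. The more serious gap is common to both. They name 420 mg as the dose to return to, whatever the reason or reasons the dose was lower. A participant can be below 420 mg for two reasons at once, an interacting antifungal and a toxicity. Stopping the antifungal removes only the first.

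Followed as written, 14.1.7 can undo a reduction made for safety, and in some cases sooner than 3.3.2 permits. This is a multi-center study, so sites could settle the matter differently, and each could point to a section in support.

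**Working it through.** No formula or stated figure is at issue. The check puts the rules side by side and follows one participant through them.

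**Inputs**

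- Standard dose: 420 mg daily (3.2).
- First hepatic toxicity, after recovery: "restart at 1 dose level below that for which the toxicity occurs (280 mg/day for 420 mg/day dose") (3.3.2.3, Table 1). The hepatic case is used because its step at the first event is unambiguous.
- "Posaconazole delayed-release capsules 300 mg once daily": ibrutinib 140 mg once daily (3.2.1).
- "Voriconazole at any dose": ibrutinib 280 mg once daily (3.2.1).

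**Main case, using only doses the protocol states**

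| Step | Rule | Dose |
|---|---|---|
| Start | 3.2 | 420 mg |
| First hepatic toxicity, recovered | 3.3.2.3, Table 1 | 280 mg |
| Posaconazole delayed-release 300 mg daily added | 3.2.1 | 140 mg |
| Posaconazole stopped, 14.1.7 followed | 14.1.7 | 420 mg |
| Posaconazole stopped, only its own reduction reversed | dose before posaconazole | 280 mg |

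Difference: 420 − 280 = 140 mg. Ratio: 420 / 280 = 1.5. Both doses apply after the antifungal has gone, so the inhibitor's own effect on exposure does not enter. Reading 1.5 as an exposure ratio would assume dose proportionality below 420 mg, whereas section 1.2.2.2 reports it for 420 to 840 mg/day.

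**Reverse order, illustrative only.** Voriconazole sets 280 mg, and hepatic toxicity then takes the dose one level down to 140 mg. When voriconazole stops, 14.1.7 again gives 420 mg. Reversing only the interaction reduction would give 280 mg, but that comparator is a construction, because the protocol has no rule for combined reductions. The main case carries the argument.

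**When the rules collide**

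- *Antifungal stops within 4 weeks of the toxicity reduction, or the toxicity has recurred.* 14.1.7 calls for 420 mg, but the conditions in 3.3.2 for going up are not met. A site cannot follow both.
- *More than 4 weeks, no recurrence.* 3.3.2 leaves the increase to the investigator and 14.1.7 says it should happen. The difference is one of direction only.
- *3.2.1 in place of 14.1.7.* Because 3.2.1 is permissive, a site can follow it together with 3.3.2. It still does not state the exception.

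**Literal reach of 14.1.7.** The sentence is not confined to antifungals that caused a dose cut. Appendix C lists fluconazole as a moderate inhibitor, and 3.2.1 keeps moderate inhibitors at 420 mg. A participant on fluconazole whose dose was cut solely for toxicity has no interaction reduction to reverse. The words of 14.1.7 would still send the dose to 420 mg when fluconazole stops. A careful clinician may reject that reading, but the text does not exclude it.

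**How often.** The documents give no frequency. Exclusion 2.1.2.7 bars a continuing need for a strong CYP3A inhibitor. The prophylactic named in 4.3, isavuconazole, is not in the dose-reduction rows of 3.2.1. Against that, 4.3 allows an alternative agent and 3.2.1 gives doses for voriconazole and posaconazole. Stopping is also foreseeable: 4.3 recommends prophylaxis above 0.20 mg/kg prednisone equivalent and leaves it to the clinician below that, while 4.1.1 intends steroids to be tapered.

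**The case against.** The best reply is contextual. The sentence in 14.1.7 follows a pointer to the CYP3A dosing table, so it is naturally read as reversing the interaction reduction, and 420 mg is the right target for someone reduced for that reason alone. *Should* is weaker than the wording used for toxicity, where reductions are required. Toxicity has its own section with its own re-escalation rule, and a clinician who gives that section priority breaks no mandatory instruction. Appendix C also names 4.4.1, which leads to 3.2.1 and its permissive wording.

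Much of this is fair. Most clinicians would probably let the toxicity rule prevail, and the outright collision is narrow. It needs an interacting antifungal, a toxicity reduction in the same participant, and a stop within 4 weeks or a recurrence. Safeguards exist as well: 3.3.2 allows discretionary reductions for bothersome toxicity, and the team discusses each participant weekly (7.5.1).

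What does not stand is the suggestion that the text resolves the matter. Even on the narrow reading, 14.1.7 fixes the target at 420 mg instead of the dose in force before the antifungal. The route through 4.4.1 ends at 3.2.1, which lacks the exception too. Appendix C names 14.1.7 as a place for instructions, so it cannot be set aside as background drug information.

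**Conclusion.** The concern holds. In a case that can arise under the protocol's own rules, 14.1.7 gives 420 mg where toxicity had set 280 mg: 140 mg, or 1.5 times, too high relative to the safety reduction. The direct conflict is between 14.1.7 and 3.3.2. Section 3.2.1 is compatible with 3.3.2 but shares the omission.

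This rests on taking 14.1.7 at its word and on Table 1 of 3.3.2.3 for the toxicity dose. No claim is made that the higher dose would cause liver harm. Section 1.2.2.2 reports an exposure-response relation for atrial fibrillation and for hemorrhage, but no association for Grade 3 or higher liver abnormalities.

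It is a minor dosing-safety inconsistency that should be fixed. The number affected is unknown and likely small. The two-stage design, its error rates, the sample size and the 6-month response endpoint are not affected.

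**What to change.** Make two edits.

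1. In 3.2.1, replace the last sentence with: *When the CYP3A inhibitor is stopped, only the reduction made for that inhibitor may be reversed; any reduction made for toxicity (3.3.2, 3.3.2.3) stays in force until the re-escalation conditions in 3.3.2 are met.*
2. In 14.1.7, replace the last sentence with a reference to section 3.2.1, as 4.4.1 already does.

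Aligning the verb in 14.1.7 with 3.2.1 would not be enough, because 3.2.1 lacks the exception as well. The cost is wording in two places, with no change to visits, sample size or analysis.

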14.1.8 Drug Dispensing

Ibrutinib will be dispensed through a qualified healthcare professional (including but not limited to, nurses, pharmacists and physicians) to a participant or Patient Care Unit for self-medication. These healthcare staff will counsel subjects prior to medication being dispensed to ensure that the subject has complied with all requirements including use of birth control and pregnancy testing (FCBP) and that the subject understands the risks associated with ibrutinib.

Ibrutinib comes packaged as 92-count and 120-count bottle sizes of 140 mg ibrutinib capsules. All unused capsules at the end of the month will be brought back and reconciled by the

Abbreviated Title: Ibrutinib for Chronic GvHD

Version Date: 4/26/2023

pharmacy. Participants will be asked to maintain a dairy and bring to the next appointment all remaining capsules.

16 APPENDICES

16.1 APPENDIX A: DIAGNOSTIC CRITERIA FOR CHRONIC CGVHD (17)

Screening/Baseline

Organ or Site	Diagnostic Features ¹	Distinctive Features ²	Others ³	Common Features ⁴
Skin	 Poikiloderma  Lichen planus-like features  Sclerotic features  Morphea-like features  Lichen sclerosis-like features	 Depigmentation  Papulosquamous lesions	 Sweat impairment  Ichthyosis  Keratosis pilaris  Hypopigmentation  Hyperpigmentation	 Erythema  Maculopapular rash  Pruritus
Nails		 Dystrophy  Longitudinal ridging, splitting, or brittle features  Onycholysis  Pterygium unguis  Nail loss ^{5,6}		
Scalp and body hair		 New onset of scarring or nonscarring scalp alopecia ⁷  Loss of body hair  Scaling	 Thinning scalp hair, typically patchy, coarse, or dull ⁸  Premature grey hair	
Mouth	 Lichen-planus-like changes	 Xerostomia  Mucoceles  Mucosal atrophy  Pseudomembranes ⁶  Ulcers ⁶		 Gingivitis  Mucositis  Erythema  Pain

Organ or Site	Diagnostic Features ¹	Distinctive Features ²	Others ³	Common Features ⁴
Eyes		 New onset dry, gritty, or painful eyes  Cicatricial conjunctivitis  Keratoconjunctivitis sicca  Confluent areas of punctuate keratopathy	 Photophobia  Periorbital hyperpigmentation  Blepharitis	
Genitalia	 Lichen planus-like features  Lichen sclerosis-like features  Vaginal scarring or clitoral/labial agglutination (females)  Phimosis or urethral/meatus scarring or stenosis (males)	 Erosions ⁶  Fissures ⁶  Ulcers ⁶		
GI tract	 Esophageal web  Strictures or stenosis in the upper to mid third of the esophagus		 Exocrine pancreatic insufficiency	 Anorexia  Nausea  Vomiting  Diarrhea  Weight loss  Failure to thrive
Lung	 Bronchiolitis obliterans diagnosed with lung biopsy	 Air trapping and bronchiectasis on chest CT	 Cryptogenic organizing pneumonia  Restrictive lung disease	

Organ or Site	Diagnostic Features¹	Distinctive Features²	Others³	Common Features⁴
Hematopoietic and immune			 Thrombocytopenia  Eosinophilia  Lymphopenia  Hypo- or hypergamma-globulinemia  Raynaud's phenomenon  Pericardial or pleural effusions  Ascites  Peripheral neuropathy  Nephrotic syndrome  Myasthenia gravis  Cardiac conduction abnormality or cardiomyopathy  Autoantibodies (AIHA and ITP)	
Muscle, Fascia, joints	 Fasciitis  Joint stiffness or contractures secondary to fasciitis or sclerosis	 Myositis or polymyositis	 Edema  Muscle cramps  Arthralgia or arthritis	

Organ or Site	Diagnostic Features¹	Distinctive Features²	Others³	Common Features⁴
Other			 Pericardial or pleural effusions  Ascites  Peripheral neuropathy  Nephrotic syndrome  Myasthenia gravis  Cardiac conduction abnormality or cardiomyopathy	

1. Sufficient to establish the diagnosis of cGVHD
2. Seen in cGVHD, but insufficient alone to establish a diagnosis of cGvHD
3. Can be acknowledged as part of the cGVHD symptomatology if the diagnosis is confirmed
4. Seen with both acute and cGVHD
5. Usually symmetric—affects most nails
6. In all cases, infection, drug effects, malignancy, or other causes must be excluded
7. After recovery from chemoradiation therapy
8. Not explained by endocrine or other causes

